## FULL PROTOCOL TITLE: The Impact of Contact Lens Coefficient of Friction (CoF) on the Development of Lid Wiper Epitheliopathy (LWE)

Korb LWE Grading				
Grading	Description	Height (%)	Width (mm)	Final score (grade)
0	no LWE	<25	<2	<0.25
1	mild LWE	25-50	2-4	0.25-1.00
2	moderate LWE	50-75	5-9	1.25-2.00
3	severe LWE	>75	>10	2.25-3.00

\*Final LWE score is the average of the LWE Height and Width

The tears collected by capillary tubes will be stored at -80°C until luminex multibead analysis. 15 µg of total protein will be analyzed for matrix metalloproteinases (MMP)-1, -2, -7, -9, -10. Pre- and post-contact lens wear concentrations of MMP will be compared for each subject. MMPs are a family of zinc proteases and an increase in MMP expression occurs in response to a wide range of stimuli, including adhesion molecules, growth factors, cytokines and hormones and is associated with ocular surface damage. The correlation coefficient, r, will be determined between LWE and the tear film levels of MMPs.

A  $p \leq 0.05$  will be considered statistically significant.

Layman's Description of Procedures	
Patient demographics	The subjects will be asked questions about their age, sex, race and ethnicity.
History	The subjects will be asked questions about their systemic health, ocular disease and surgical history.
Concomitant Medications	The subjects will be asked questions about their current ocular and systemic medications.
Habitual Contact Lens Information	The subjects will be asked questions about how they use their current contact lenses, such as their current contact lens brand and wear time, as performed during a normal eye exam.
Auto-refraction	A machine will shine light into a subject's eye and will estimate their prescription using different powered lenses without making contact with the eye.
Oculus Keratograph	A machine uses a video camera to determine how long it takes for a subject's tear film to

**FULL PROTOCOL TITLE: The Impact of Contact Lens Coefficient of Friction (CoF) on the Development of Lid Wiper Epitheliopathy (LWE)**

	evaporate and the height of the pooled tears between the lower lid and the ocular surface without making contact with the eye.
Phenol Red Thread	A small thread containing a pH indicator that turns from red to yellow when it contacts tears will be placed at the subject's lower lid margin and left for 15 seconds. The length that the tears have traveled will be measured. This test does not require anesthesia.
Slit Lamp Exam	A specialized microscope is used to shine light on the eye and to examine the health of the eyelids and the front of the eye.
Subjective Refraction/Spherical Equivalent Refraction	The subject's prescription is determined by placing different power lenses in front of the subject's eye, according to the subject's responses.
Contact Lens Fitting	A contact lens is placed on the eye and the fit is assessed (how much it moves, where it sits on the eye, etc.). This is done using a slit lamp biomicroscope.
Contact Lens Over-Refraction and Power Adjustment	Lenses will be placed in front of the subject's eye while wearing the study contact lenses to determine if the prescription needs to be changed according to the subject's responses. The contact lens power will be adjusted if needed.
Questionnaire: Ocular Surface Disease Index (OSDI)	The questionnaire asks the subject's vision during various tasks, eye pain, comfort in various environments, etc.

# **FULL PROTOCOL TITLE: The Impact of Contact Lens Coefficient of Friction (CoF) on the Development of Lid Wiper Epitheliopathy (LWE)**

## **9.0 Setting**

All study visits will be conducted at the University of Houston College of Optometry at The Ocular Surface Institute (TOSI) within the Human and Biological Sciences Building.

## **10.0 Drugs or Devices**

No investigational medical devices or investigational ophthalmic pharmaceuticals will be assessed in this study. The contact lenses fit in the study (Acuvue Oasys, Johnson & Johnson Vision Care; Air Optix Night and Day Aqua, Alcon Laboratories) are commercially available, FDA approved contact lenses that will be fit per the manufacturers recommended fitting guide on a daily wear basis (i.e. subjects will not sleep in lenses). The ophthalmic drops used in the trial to evaluate LWE (sodium fluorescein, lissamine green) are commercially available ocular diagnostic agents commonly used in clinical practice.

## **11.0 Risks to Subjects**

The risks to the subjects in the trial are the same risks found in standard clinical practice. During study procedures, there is the risk of mild ocular discomfort during clinical procedures due to light being shined on the eye (e.g. Slit lamp biomicroscopy), by being asked to not blink for a short period of time during a procedure (e.g. Oculus Keratograph NITBUT), during surface tear collection or through the use of topical ophthalmic diagnostic agents (sodium fluorescein, lissamine green). Potential discomfort from these procedures is transient and self-limiting.

Contact lenses will be fit as part of this study. The US Food and Drug Administration consider daily wear contact lenses Class II medical devices. While most individuals wear contact lenses successfully without incident, problems with contact lenses or lens care products can result in serious injury to the eye. Ulcerative keratitis (infection of the cornea), can develop rapidly and lead to loss of vision. Ulcerative keratitis is estimated to happen to about 4.1 out of 10,000 people who use daily wear contact lenses. The overall risk of ulcerative keratitis may be reduced by carefully following directions for lens care, and subjects in the study will be educated on proper contact lens use and care.

The following problems may also occur when wearing contact lenses:

- Burning, stinging, and/or itching of the eyes
- Less comfort after daily wear than when the lens was first placed on the eye
- A feeling like there is something in the eye (foreign body, scratched area)
- Reduced vision or temporary loss of vision due to peripheral infiltrates (white blood cells), peripheral corneal ulcers (inflammation of the cornea), and/or corneal erosion (defects in the corneal surface)
- Local or generalized edema (swelling)

## **FULL PROTOCOL TITLE: The Impact of Contact Lens Coefficient of Friction (CoF) on the Development of Lid Wiper Epitheliopathy (LWE)**

- Corneal neovascularization (small blood vessels growing into the cornea)
- Corneal staining (defect in the corneal surface)
- Redness
- Tarsal abnormalities (bumps on the inside upper eye lid)
- Iritis (internal inflammation of the eye)
- Conjunctivitis (infection or inflammation of the white part of the eye or under the eyelids)
- Excessive watering, unusual eye secretions, or redness of the eye
- Poor visual acuity
- Blurred vision
- Rainbows or halos around objects
- Sensitivity to light
- Dry eyes may also occur if lenses are worn continuously or for too long a time

Many of the potential problems associated with contact lens wear are self-limiting and can be resolved with discontinuation of lens wear. These problems can be minimized or avoided with proper contact lens fitting and follow-up. Subjects in the study will be examined approximately 7 days after contact lens fitting, which is typical in clinical practice for contact lenses worn in a daily wear modality.

Subject safety will be monitored in the trial through slit lamp evaluation of the ocular surface. Subjects will be educated to potential risk with contact lens wear and instructed to discontinue contact lens wear and contact the study investigators if they experience any eye discomfort, excessive tearing, vision changes, redness of the eye, or other problems.

**Subjects will be instructed that in the event they experience signs or symptoms associated with a potential adverse event, they should contact the study personnel immediately for evaluation.**

### **12.0 Potential Benefits to Subjects**

There is no direct benefit that the individual subjects may experience from taking part in the research; however, participation in the trial may lead to clinical insights that could potentially predict future contact lens comfort in patients.

### **13.0 Withdrawal of Subjects**

Subjects may withdraw consent to participate in the study at any time. Subjects may be withdrawn from the trial by the study investigators if they are lost to follow up (fail to complete Visit 2 within the allotted time period), become pregnant during the trial, have a study-related adverse event that warrants study withdrawal or they fail to follow the study instructions.

### **14.0 Costs/Payments to Subjects**

## **FULL PROTOCOL TITLE: The Impact of Contact Lens Coefficient of Friction (CoF) on the Development of Lid Wiper Epitheliopathy (LWE)**

There are no expected additional costs to subjects that participate in the study. There is no cost to subjects for contact lens fitting in this study. Subjects will be provided contact lenses and care solution at no cost for the duration of the study. Subjects will be provided with a token for parking at each study visit (if necessary). Subjects that complete contact lens fitting (i.e. that is completes both study Visit 1.1 and 1.2) will be compensated \$30. Subjects who complete the 1-week follow up will be compensated \$10. If subjects are determined ineligible at screening (screen fail), the subject will be compensated \$5, with the opportunity for a total of 3 re-screenings at the investigators discretion. Total subject reimbursement (without rescreening visits) will be \$40. Subjects will be compensated using Amazon electronic gift cards in the amounts indicated above, delivered to the subject via an e-mail address provided by the subject, after completion of their last study visit. Subjects who fail to complete a visit will not be compensated for that visit. Subjects will be instructed to contact the study PI in the event that they do not receive the electronic gift card.

### **15.0 Compensation for Research-Related Injury**

The risks to subjects from participation in the study are minimal. The clinical procedures used in the study (slit lamp biomicroscopy, non-invasive tear break up time) are commonly used clinical procedure in optometry and ophthalmology and may cause some discomfort due to light shining on the surface of the eye, during ocular surface tear collection or during contact lens wear. In the rare case that a subject is injured as part of their participation in the study, the subject will be responsible for any associated medical bills.

### **16.0 Confidentiality**

Subjects will be assigned a unique subject ID. Subjects IDs are two digits and should start at 01 and continue in the order of enrollment. No one outside of the research team will have access to the subject identifiers. A key to the study code will be maintained for 3 years at the time of study completion (i.e. Last Subject, Last Visit).

Any source documents with patient identifiable information will be kept only at the local site (informed consent form, linking log). Individual documents will be kept in a secure room in the Ocular Surface Institute (TOSI).

### **17.0 Provisions to Protect the Privacy Interests of Subjects.**

Those who are potentially eligible and interested in the study will be referred to a study investigator or coordinator who will discuss the study with the patient. This discussion will take place in a quiet, private area and as much time as necessary will be spent discussing the details of the study.

## **FULL PROTOCOL TITLE: The Impact of Contact Lens Coefficient of Friction (CoF) on the Development of Lid Wiper Epitheliopathy (LWE)**

### **18.0 Informed Consent Process**

The participant will be provided an opportunity to read the informed consent and to have any questions answered before agreeing to participate. Prior to any testing, the investigator or study coordinator will obtain written informed consent from all participants. The consent form will be signed and dated by both the participant and a member of the study personnel who has been approved to obtain consent. The participant will receive a copy of the signed consent documents and the originals will be filed in the subject binder on site in a secure location.

### **19.0 HIPAA**

We will be collecting demographic information along with general medical and eye health information. Since protected health information will be collected, the Health Insurance Portability and Accountability Act (HIPAA) authorization form will be included as part of the Informed Consent process.

The linked PHI will be destroyed upon completion of the study. PHI will not be reused or disclosed to any other person or entity, except as required by law, for authorized oversight of the research study, or for other research for which the use or disclosure of protected health information for which an authorization or opportunity to agree or object is not required by 45 CFR 164.512.

### **20.0 Data Management**

Paper source documents (i.e. case report forms) will only be associated with a subject ID number and will not contain direct subject identifiers.

### **21.0 Specimen Use and Banking**

The tear specimens will be stored in a -80°C freezer until luminex multibead analysis. The specimens will be stored for up to 3 months. The principal investigators and other members of the research team will have access to the specimens.

### **22.0 Sharing of Results with Subjects**

There are no plans to share study results with subjects as it will not directly benefit their eye/vision health. If findings are discovered during the trial that potentially have an impact on the subject's health or wellbeing, the subject will be educated to these findings.

### **23.0 Resources**

## **FULL PROTOCOL TITLE: The Impact of Contact Lens Coefficient of Friction (CoF) on the Development of Lid Wiper Epitheliopathy (LWE)**

The study team completed all necessary ethics training requirements. The co-PIs ([name], OD, PhD and [name], OD, PhD) have over a decade of clinical research experience conducting clinical studies and will oversee the other study personnel.

The number of subjects to be recruited is based on the typical number of subjects needed to approach the central limit theorem. With an abundance of contact lens wearers in the surrounding community, we believe that we should be able to complete enrollment within 3 months.

This study utilizes the clinics of The Ocular Surface Institute to see study subjects on the campus of the University of Houston.

## **FULL PROTOCOL TITLE: The Impact of Contact Lens Coefficient of Friction (CoF) on the Development of Lid Wiper Epitheliopathy (LWE)**

### Addendum: Statistical Analyses

Statistical analyses were performed in SPSS v26 (IBM) and GraphPad. When data were not significantly different from a normal distribution (non-invasive tear break up time, tear meniscus height), statistical analyses were conducted using paired t-tests and repeated-measures analyses of variance (RM-ANOVA), with adjusted post-hoc t-tests, when appropriate. For NITBUT and TMH, the RM-ANOVA included two repeated factors—lens type (Acuvue Oasys and Air Optix Night and Day) and time (baseline, 2 hours post-fitting and 7 days after lens fitting). For data that was not normally distributed (LWE staining), Friedman and Mann-Whitney non-parametric statistics were performed. MMP concentrations were adjusted by multiplying raw values by the dilution factor. Tear film MMP concentrations under the level of detection (LOD) were divided by  $\sqrt{2}$  (Croghan et al. 2003). Outliers in MMP data sets were analyzed using the ROUT function in Graphpad Prism 8.4.1 and were removed prior to analysis.

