### Sequence of Events

## FULL PROTOCOL TITLE: The Impact of Contact Lens Coefficient of Friction (CoF) on the Development of Lid Wiper Epitheliopathy (LWE)

Note: Contact Lens wearing subjects should report to Visit 1 after discontinuing SCL wear for at least 7 days. Subjects should report to the visit wearing their habitual vision correction.

Visit 1.1: Screening, Enrollment and Baseline		
Step	Item	Details
1.1.1	Informed Consent	Review and complete the informed consent form
1.1.2	Subject Demographics	Collect subject demographic data
1.1.3	History	Collect subject history
1.1.4	Concomitant Medications	Collect information on concomitant medications
1.1.5	Habitual Contact Lens Information	For CL subjects, review habitual lens information and verify that they have discontinued lens wear for at least 7 days
1.1.6	Preliminary Review of Inclusion/Exclusion Criteria	Review Inclusion/Exclusion Criteria for subject study eligibility
1.1.7	Distance Visual Acuity	Perform Distance, High Contrast Visual Acuity using Snellen optotype, OD/OS with the patient's habitual correction.
1.1.8	Questionnaires: Ocular Surface Disease Index (OSDI)	All Subjects: Administer the OSDI 
 
• If OSDI scores is <math>\geq 23</math>; skip to 2.9, Final Evaluation
 

1.1.9	Auto-refraction	Perform auto-refraction and record the refractive error and keratometry readings
1.1.10	Oculus Keratograph	Perform the following procedures using Oculus Keratograph, OD/OS 
 
• Non-invasive Tear Break Up Time (NITBUT)
 
• Tear Meniscus Height
 

1.1.11	Phenol Red Thread	Perform Phenol Red Thread test without anesthesia, OD/OS.
1.22	Ocular Surface Tear Collection	Collect 10 $\mu$ L surface tears using a microcapillary tube.
1.1.12	Slit Lamp Exam with vital dye staining/LWE evaluation	Instill 1 drop of NaFL + Lissamine Green Combination Drop, wait 5 minutes, instill an additional drop, wait 1 minute, then evaluate slit lamp findings using the CCLRU grading scale and evaluate LWE

**FULL PROTOCOL TITLE: The Impact of Contact Lens Coefficient of Friction (CoF) on the Development of Lid Wiper Epitheliopathy (LWE)**

		
 
• If no LWE is observed in both eyes, skip to Step 2.9: Final Evaluation and discontinue the subject from the trial
 
• If LWE is observed in either eye, continue to Step 1.1.13: Digital Photography
 

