1.1.13	Digital Photography	Perform Digital Photography of the Lid Wiper region OD/OS
1.1.14	Subjective Refraction	
Perform Manifest Refraction using maximum plus to best visual acuity.
 
 
• If the subject has <math>> 1.00\text{D}</math> refractive cylinder or greater than 1D of anisometropia, skip to Step 2.9: Final Evaluation and discontinue the subject from the trial
 

1.1.15	Subjective Spherical Equivalent Refraction	Perform Subjective Spherical Equivalent using maximum plus to best visual acuity.
1.1.16	Contact Lens Fitting	
Fit subject in contact lenses based upon the randomization schedule. Initial base curve should be selected as indicated in the fitting guide for each lens.
 
 
• If an acceptable contact lens fit cannot be obtained in either eye, skip to Step 2.9: Final Evaluation and discontinue the subject from the trial
 

1.1.17	Contact Lens Over-Refraction	Perform spherical over-refraction using maximum plus to best visual acuity
1.1.18	Contact Lens Power Adjustment (if necessary)	Modify contact lens power, based upon the Contact Lens Over-Refraction, if the subject gains 3 or more letters acuity
1.1.19	2 hour Waiting Period	Subjects released to waiting area for 2 hours

**FULL PROTOCOL TITLE: The Impact of Contact Lens Coefficient of Friction (CoF) on the Development of Lid Wiper Epitheliopathy (LWE)**

Visit 1.2 Note: Visit should be performed approximately 2 hours after lens insertion		
1.2.1	Visual Performance	Perform logMAR visual acuity
1.2.2	Oculus Keratograph	Perform the following procedures using Oculus Keratograph with the contact lens on eye, OD/OS 
 
• Non-invasive Tear Break Up Time (NITBUT)
 
• Tear Meniscus Height
 
• Video Contact Lens Fit
 

1.2.3	Ocular Surface Tear Collection	Collect 10µL surface tears using a microcapillary tube.
1.2.4	Contact Lens Removal	Remove the contact lenses and store in solution
1.2.5	Slit Lamp Exam with vital dye staining/LWE evaluation	Instill 1 drop of NaFL + Lissamine Green Combination Drop, wait 5 minutes, instill an additional drop, wait 1 minute, then evaluate slit lamp findings using the CCLRU grading scale and evaluate LWE

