## FULL PROTOCOL TITLE: The Impact of Contact Lens Coefficient of Friction (CoF) on the Development of Lid Wiper Epitheliopathy (LWE)

Visit 2: 1-Week Follow Up ( $\pm 2$ days) Note: Subjects should report to Visit 2 wearing their study assigned soft contact lenses.		
2.1	History	Collect subject history, compliance and reported wearing time
2.2	Visual Performance	Perform logMAR Visual Acuity
2.3	Questionnaires	Administer the OSDI to the subject
2.4	Oculus Keratograph	
Perform the following procedures using Oculus Keratograph (lens on eye for CL patients, bare eye for non-CL patients, OD/OS)
 
 
• Non-invasive Tear Break Up Time (NITBUT)
 
• Tear Meniscus Height
 
• Video Contact Lens Fit
 

2.5	Ocular Surface Tear Collection	Collect 10 $\mu$ L surface tears using a microcapillary tube.
2.6	Contact Lens Removal	Remove the contact lenses and store in solution
2.7	Slit Lamp Exam with vital dye staining/LWE evaluation	Instill 1 drop of NaFL + Lissamine Green Combination Drop, wait 5 minutes, instill an additional drop, wait 1 minute, then evaluate slit lamp findings using the CCLRU grading scale and evaluate LWE
2.8	Digital Photography	Perform Digital Photography of the Lid Wiper region OD/OS
Final Evaluation		
2.9	Exit Visual Acuity	Perform Distance, High Contrast Visual Acuity using Snellen optotype with the patient's habitual correction.
2.10	Final Evaluation Form	Complete the final evaluation form and indicate if the subject successfully completed the study
2.11	Protocol Deviations	Ensure any protocol deviations have been recorded

The procedures involved in the study are common clinical procedures found in Optometry/Ophthalmology. LWE assessment will occur following installation of sodium fluorescein and lissamine green ophthalmic drops. The upper and lower lids will be photographed using a slit-lamp biomicroscopy and a camera.

Photographs will be de-identified and graded subjectively for LWE using the Korb scale (see below). Photos may also be analyzed for objective LWE grading using custom coding in MATLAB.

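### For NITBUT and TMH, counting the pre-fitting baseline as a level of time cuts the expected lens main effect to two thirds of the post-fit difference, and the addendum does not say which term answers the lens question

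*Combined protocol and SAP*

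**What the plan says.** The section Addendum: Statistical Analyses states: "For NITBUT and TMH, the RM-ANOVA included two repeated factors", namely lens type and "time (baseline, 2 hours post-fitting and 7 days after lens fitting". It also lists paired t-tests and, where judged appropriate, adjusted post-hoc t-tests. It mentions no lens-by-time interaction, no contrast limited to the post-fit times and no baseline covariate.

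The visit schedule in protocol section 8.0 fixes the condition of the eye at each reading:

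- **Baseline, Step 1.1.10:** "Perform the following procedures using Oculus Keratograph, OD/OS". Lenses are first applied later, at Step 1.1.16: "Fit subject in contact lenses based upon the randomization schedule". Previous wearers come without recent soft lens wear: "Contact Lens wearing subjects should report to Visit 1 after discontinuing SCL wear for at least 7 days".
- **2 hours, Step 1.2.2:** "Perform the following procedures using Oculus Keratograph with the contact lens on eye, OD/OS".
- **7 days, Step 2.4:** the condition is "lens on eye for CL patients, bare eye for non-CL patients, OD/OS". The Visit 2 note says "Subjects should report to Visit 2 wearing their study assigned soft contact lenses", and the lenses come off only at Step 2.6.

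Section 1.0 assigns the two lenses to a subject's eyes at random. NITBUT and TMH appear in neither the hypotheses of section 1.0 nor the endpoints of section 7.0.

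**The concern.** At one of the three time levels neither eye carries the lens that its lens-type label names. The lens main effect averages over all three levels, so it mixes two informative differences with one whose expectation is zero. Taken as the answer to whether the lenses differ in tear stability or meniscus height, it understates the difference and may miss it.

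The time factor has a related problem. The step from baseline to 2 hours changes the surface being measured, from bare eye to lens on eye, as well as the elapsed time. A significant time effect could then be misread as an effect of wear.

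**Working it through.** **No figure to reproduce.** Section 5.0 sets a goal of 20 completers and waives a power analysis. The documents give no effect size, SD or correlation for NITBUT or TMH.

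**Expected lens main effect.** Let d₀, d₂ and d₇ be the expected between-lens differences at baseline, 2 hours and 7 days. Random eye assignment before any lens wear gives d₀ = 0.

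- Three-level main effect: (0 + d₂ + d₇)/3.
- Mean post-fit difference: (d₂ + d₇)/2.
- Ratio: (1/3)/(1/2) = 2/3, whether or not d₂ = d₇. For example, d₂ = 0.5 and d₇ = 1.0 give 0.50 against 0.75.

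**Power, under assumptions.** In a balanced within-subject design the lens main-effect test is a paired t-test on each subject's averaged between-eye difference. Assume n = 20, two-sided 0.05 (the threshold is in section 8.0; sidedness is not stated), d₂ = d₇ = d = 0.6 SD of the between-eye difference, equal SDs at each time, and a common correlation r of those differences over time. The noncentrality parameters, with √20 = 4.472, are:

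- Three levels: (2/3)d√n / √((1+2r)/3) = 1.789 / √((1+2r)/3)
- Two post-fit levels: d√n / √((1+r)/2) = 2.683 / √((1+r)/2)
- Post-fit, adjusted for the baseline difference: 2.683 / √((1+r)/2 − r²)
- Lens-by-time interaction, F on 2 and 38 df: n(2d²/3)/(1−r) = 4.8/(1−r)

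| r | Three-level lens main effect | Two post-fit times | Post-fit, baseline-adjusted | Interaction |
|---|---|---|---|---|
| 0 | 3.10 → 84% | 3.79 → 95% | 3.79 → 95% | 4.8 → 46% |
| 0.5 | 2.19 → 55% | 3.10 → 84% | 3.79 → 95% | 9.6 → 76% |
| 0.8 | 1.92 → 45% | 2.83 → 77% | 5.26 → above 99% | 24 → 99% |

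The adjusted column treats the baseline slope as known, so it is slightly optimistic. The squared ratio of the first two noncentralities is 2/3 at r = 0 and 1/2 at r = 0.5. The loss is thus equivalent to one third or one half of the sample.

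The loss varies with the assumptions. At d = 0.8 and r = 0 it is small (97.5% against 99.8%); at d = 0.5 and r = 0.8 it is large (33% against 61%).

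**If baseline is uncorrelated with the lens-on readings.** Bare-eye and lens-on readings may differ in kind. Take baseline correlation 0 and post-fit correlation 0.5. The variance of the three-level average is (3 + 2×0.5)/9 = 4/9, the noncentrality is 1.789/0.667 = 2.68, and power is 72%. The two post-fit times still give 84%, and adjustment adds nothing (83%).

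**Time effect.** Split its 2 df into bare eye versus lens-on, (2, −1, −1)/√6, and 2 hours versus 7 days, (0, 1, −1)/√2. With illustrative means (0, −1, −1.3) the squared components are (2.3)²/6 = 0.882 and (0.3)²/2 = 0.045, so lens presence accounts for 0.882/0.927 = 95%. The share is 100% with means (0, −1, −1), and 75% with (0, −1, −0.5) or (0, −1, −2).

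**The case against.** The strongest reply is that a factorial model should not be judged by one term. With a pre-treatment level in the design, a lens effect also appears in the lens-by-time interaction, which a two-factor RM-ANOVA ordinarily produces. At r = 0.5 the interaction has 76% power, and its baseline-versus-post-fit contrast has 84%, the same as the two post-fit times. A paired t-test between lenses at a single post-fit visit carries no dilution and has 72% power before any multiplicity adjustment (noncentrality 0.6√20 = 2.68). This stands, and it rules out the inference that the analysis cannot detect a lens difference.

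It does not remove the point. The addendum does not name the interaction, does not say which comparisons the t-tests made, and does not say which result decides the lens question. If post-hoc tests follow only a significant main effect, they inherit the dilution. The interaction is also weak at low correlation (46% at r = 0).

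A reader might also infer that the time effect is nothing but bare eye versus lens-on, or that the authors interpreted it as wear. The documents support neither: the 2-df test also contains 2 hours versus 7 days, and the addendum offers no interpretation of time.

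It is also fair that this is a pilot without a power analysis and that NITBUT and TMH are not named endpoints. That limits the reach of the point but does not make it wrong.

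**Conclusion.** The point holds for NITBUT and TMH only. The two-thirds factor is exact in expectation and rests on random eye assignment and on no study lens being worn at baseline. Step 1.1.10 does not use the words bare eye; that is inferred from the order of the steps and the 7-day washout.

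The power figures are illustrative, because effect size and correlation are assumed. At d = 0.6 the three-level lens main effect falls short of the two post-fit times by 11 points at r = 0 (84% against 95%), 29 points at r = 0.5 (55% against 84%) and 32 points at r = 0.8 (45% against 77%).

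The time effect is largely, but not wholly, confounded with lens presence. It would be too strong to call the lens test invalid: if the lenses truly do not differ, all three expected differences are zero, so the dilution costs size of effect and power, not false positives. Nor does the point touch the primary outcome, which the addendum analyses by non-parametric methods.

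**What to change.** Take the lens effect on NITBUT and TMH from the two lens-on times, 2 hours and 7 days, and name that contrast as the one that answers the lens question. Adjust for baseline in one of two ways: regress the averaged post-fit between-eye difference on the between-eye baseline difference, or fit a mixed model with each eye's baseline as covariate. Classical RM-ANOVA does not take a covariate that varies between a subject's eyes, so one of these must replace it. Report 2 hours versus 7 days as the time comparison, and do not interpret change from baseline to post-fit as an effect of wear.

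The addendum is written in the past tense, so the cost is a small re-analysis plus revised wording. No new data are needed.

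Separately, reconcile the bare-eye clause for non-CL patients in Step 2.4 with the Visit 2 note that subjects arrive in study lenses. If the clause was applied to neophytes, the 7-day level mixes two measurement conditions, and the records should show which condition was used.
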